7.4 Withdrawal criteria

A subject should be withdrawn from treatment if they meet the discontinuation criteria in Section 9.8. If a subject is discontinued at any time after entering the study the investigator will make every effort to see the subject and complete the early termination visit assessments.

Subjects may withdraw from the study at any time without stating a reason and without prejudice to further treatment. The Investigator may withdraw a subject from the study and discontinue study treatment and assessments at any time.

Early discontinuation of any subject who has given informed consent to participate will be recorded including the reason for discontinuation. The primary reason for a subject withdrawing prematurely will be selected from the following standard categories of early discontinuations:

- **Failed to meet randomization criteria**
- **Adverse Event (Adverse Reaction):** Clinical events occurred or laboratory results are reported that in the medical judgment of the investigator are grounds for discontinuation in the best interests of the subject.
- **Withdrawal of Consent:** The subject desired to withdraw from further participation in the study. The subject is not obliged to provide any reason for withdrawal of consent, but where a reason is given this will be recorded on the eCRF.
- **Protocol Violation:** The subject failed to adhere to the protocol requirements, at the investigator's discretion e.g. the subject needs to start taking a medication from the prohibited medications list (Section 9.13.2).

- **Lost to Follow-Up:** The subject stopped coming for visits and study personnel were unable to contact the subject.
- **Other:** The subject was terminated for a reason other than those listed above, such as theft or loss of study drugs or electronic equipment or termination of study by Sponsor.

All subjects who withdraw from the study may be replaced.

8. STUDY DESIGN

8.1 Pharmacokinetic endpoints

- Pharmacokinetics of NT-814: Peak concentration (C_{max}), time of occurrence of C_{max} (t_{max}), area under the curve (AUC) from time zero (pre-dose) to the time of the last quantifiable concentration (AUC_{0-t}), AUC in the dosing interval at steady state $AUC_{0-\tau}$ (AUC_{0-24}) after single and repeat dosing, apparent terminal phase half-life ($t_{1/2}$), AUC from time zero (pre-dose) extrapolated to infinity ($AUC_{0-\infty}$) after single dose, and apparent clearance (CL/F).

8.2 Safety endpoints

Safety and tolerability will be assessed by the following:

- Physical Examinations
- Analysis for arrhythmias as assessed by continuous Holter monitoring from Day -1 to Day 8 (24 hours post Day 7 dose) and Day 14 (24 hours)
- Abnormalities on the 12-lead ECGs
- Change in ECG variables (heart rate, RR, PR, QRS, QT, QTcF and QTcB)
- Change from Baseline in clinical laboratory assessments including lipids and coagulation profile
- Change from baseline in hormones including estradiol, testosterone, follicle stimulating hormone (FSH), adrenocorticotropic hormone (ACTH), cortisol, thyroid-stimulating hormone (TSH), triiodothyronine (T3) and thyroxine (T4)
- Change from Baseline in vital signs including oxygen saturation, oral temperature and postural blood pressure (BP) changes
- Adverse events (AEs) of dehydration (supported by changes in serum urea and creatinine, urinary sediment and weight and vital signs)
- Nature and severity of Adverse Events (AE)
- Withdrawals due to AEs

8.3 Exploratory endpoints

- Change in frequency of hot flashes from Pre-dose (Day -1) as assessed by skin conductance
- Change from Baseline in frequency of moderate to severe hot flashes, hot flash average severity and hot flash severity score as measured by twice daily paper diary throughout study
- Change in frequency of hot flashes as measured by continuous day time diary from Day -1 pre-dose to Day 7 and Day 14
- Change from Baseline in night-time-awakenings (NTA) secondary to hot flashes as measured by paper diary
- Change in LH AUC_{0-8 hours} on Day-1 versus Day 1 and Day 7
- To explore the relationship between plasma concentrations and placebo-corrected change from baseline QTcF and QTcB values using concentration effect modeling, depending on the results observed

8.4 Study design

This is a multi-center, double-blind, randomized, placebo-controlled multiple ascending dose trial in post-menopausal women with vasomotor symptoms.

Subjects will be recruited into a maximum of 5 sequentially dosed cohorts; Cohort 1 (50 mg NT-814), Cohort 2 (100 mg NT-814), Cohort 3 (150 mg NT-814) and, if needed, 2 further cohorts up to 400mg NT-814. See [Figure 1](#) for study design schematic.

For each cohort, subjects will enter a 4 week screening period to determine eligibility. Twenty eligible subjects will be randomized per cohort (15 active and 5 placebo).

During the screening period each subject will be required to complete twice daily paper diaries. Eligible subjects will demonstrate, at the Baseline visit, an average 24-hour moderate to severe hot flash frequency ≥ 7 and ≤ 20 based upon the average daily frequency of all available readings (at least 4 days) in the final week of screening (Week -1). If at the Baseline visit subjects have an average 24-hour hot flash frequency < 7 /day or > 20 /day they will be discontinued from the study. In addition, subjects that have a change of $\geq 50\%$ in average 24-hour hot flash frequency between the first and second week of the screening period (Week -2 and Week -1 respectively) will be excluded. Subjects will also be provided with the continuous daily diary during screening and instructed to start completing this on the morning of Day -1 after waking, prior to admission to the clinic, and to continue to complete this throughout Day -1.

It may be necessary to extend a patient's screening period beyond 28 days (with the approval of the sponsor) when a subject is held over from one cohort to the next because the original cohort into which they would have been enrolled is complete. If this occurs, the following safety procedures must be repeated such that the most recent evaluation occurs within 28 days of the rescheduled randomization:

- Biochemistry and hematology
- Vital signs
- 12-lead ECG
- Physical examination

If the subject has completed (or partially completed) the screening twice daily Hot Flash Diary this must still be repeated and a new diary started on the new planned Day -15 and completed for the 2 weeks up to Day -2. Eligibility will be assessed on the repeated diary, not the initial one. If the subject had not started completing their screening diary at the time screening was put on hold, they will start this screening diary on the re-scheduled Day -15.

Eligible subjects will be admitted to a Phase 1 Unit as an inpatient on the morning of Day -1 and will be fitted with and instructed on use of a sternal skin conductance monitor and Holter monitor which will be worn continuously until discharge from the clinic on Day 8; both the Holter monitor and sternal skin conductance monitor will be refitted on return to the Phase 1 Unit on Day 14. Routine safety monitoring will be carried out in a manner that will form the baseline for comparisons for the remainder of the study.

On Day 1, the subjects will be randomized in a 3:1 ratio to once daily (morning) doses of NT-814 or placebo, to be taken for a total of 14 days. Subjects will be monitored as an inpatient from Day -1 to Day 8 and will undergo blood draws for intensive PK sampling, safety monitoring and for impact on blood hormonal profiling as well as 24-hour skin conductance measurements and continuous completion of hot flash diaries.

Subjects will be discharged from the clinic on Day 8 without any monitoring devices, providing there are no safety concerns and will undergo dosing for a further 5 days as an outpatient. Subjects will be instructed to continue recording details of the hot flashes experienced, using the twice daily diary. They will be provided with the continuous daily diary and instructed to start completing this upon waking on the morning of Day 14 prior to admission to the clinic. They will be re-admitted to clinic on the morning of Day 14 for the final dose and undergo the same assessments with the same devices including Holter and skin conductance as Day 1. Subjects will be discharged following the 24-hour post Day 14 assessments (Day 15). Subjects will return to the clinic, as outpatients, for a single PK sample on the mornings of Days 16 and 17 (48 hours and 72 hours after the Day 14 dose respectively).

Throughout the study, subjects will be closely monitored for safety including assessments of AEs, 12-lead ECGs, atrial oxygen saturation using pulse oximetry, vital signs (sitting and standing BP, heart rate, oral body temperature, and respiration rate), clinical labs and physical examinations.

At the end of each Cohort a blinded review of PK and safety data from all subjects will be conducted by the Safety Review Committee (see Section 10.7) to confirm that it is safe to proceed to the next

dose. This review must comprise complete data up to Day 17 from a minimum of 14 subjects per cohort.

In the case of any safety concern or any ambiguous data, from any one of the cohorts, either individual subjects or the entire cohort may be unblinded to enable decision making. In this eventuality a separate un-blinded Safety Review Committee will be used to maintain the integrity of following cohorts if needed. Details are outlined in the Safety Review Committee Charter.

Subjects may not participate in more than one Cohort.

A final Follow-up visit will be conducted by phone one week after completion of dosing for each Cohort, unless a clinic visit is deemed more appropriate by the Investigator in order to follow up any ongoing adverse events.

9. STUDY MEDICATION AND ADMINISTRATION

9.1 Study medication

The test product, NT-814A in the free base form, formulated as a 50 mg dose in opaque white / white hard gelatin capsules to be taken orally once-daily. The physical, chemical, pharmaceutical formulation properties and characteristics of NT-814 are described in the IB.

The planned dosing schedule is as detailed in [Table 1](#).

Table 1: Dosing schedule

| | |
|----------|-----------------------------|
| Cohort 1 | 50 mg (1 x 50 mg capsule) |
| Cohort 2 | 100 mg (2 x 50 mg capsules) |
| Cohort 3 | 150 mg (3 x 50 mg capsules) |
| Cohort 4 | TBD |
| Cohort 5 | TBD |

Matching placebo capsules will be used as the reference treatment in this study and will be administered as for the test product.

Subjects will take capsule(s) once a day in the morning on an empty stomach and should not eat anything for 4 hours following administration. Subjects will be required to fast from midnight prior to dosing on Days 1,7 and 14, and for up to 4 hours after (see Section 9.13.3).

Subjects will receive doses on Days 1 to 8 whilst at clinic. On Day 8, subjects will be dispensed 5 days' supply for self-administration at home on Days 9 to 13, along with an Investigational Medicinal Product (IMP) administration diary which they will be asked to complete. Subjects will be asked to return the remaining medication when they return to the clinic. The Day 14 dose will be administered in the clinic.

If subjects forget to take a dose when at home they will be instructed to miss that dose and take the next dose as scheduled.

9.2 Selection of doses in the study

To date 90 volunteers (including only 1 female) have been dosed with NT-814 with single doses up to 250 mg once daily (OD) with 15 subjects being dosed with a total daily dose of 200 mg for up to 29 days in the repeat dose human safety study (MNK111587) where attained exposures up to a

maximum AUC₀₋₂₄ of 41900 ng.h/mL were considered safe and well tolerated. A PK/PD model was created using serum total testosterone levels as a marker of target engagement from data from the Phase 1 studies. Based upon this model a mean AUC of 14040 ng.h/mL predicts near maximal target engagement at the NK₃ receptor. This exposure was achieved in male subjects following doses of 200 mg for 28 days.

The objective of this study is to characterize the PK and safety of NT-814 in a controlled setting in post-menopausal women with vasomotor symptoms to inform future development in this population using a target of maximum exposures of around 15000 ng.h/mL. To achieve the target PK AUC exposure objective, the study will be conducted in a controlled Phase 1 Unit setting with close safety monitoring and using predefined stopping criteria outlined in Section 9.9 as well as pre-defined PK stopping limits outlined below and will consist of a maximum of 4 sequentially dosed cohorts: Cohort 1, Cohort 2, Cohort 3 and if needed Cohorts 4 and 5. Planned dose escalation steps for the first 3 cohorts are in multiples of 50 mg NT-814 starting with an initial dose of 50 mg. Subsequent doses will be based on PK modelling of data from the first 3 cohorts increasing to a maximum dose of 400 mg if appropriate and needed. The predicted exposure increase between Cohorts 3 and 4 and between Cohorts 4 and 5 (if applicable) will be ≤ 2 fold. In the one-month monkey toxicity study, the effect level was considered as 60 mg/kg/day and this corresponded to a geometric mean AUC₀₋₂₄ of 35700 ng.h/mL. However, exposures up to a maximum AUC₀₋₂₄ of 41900 ng.h/mL were safe and well tolerated in the repeat dose human safety study (MNK111587); and this maximum value is used as the basis of safety margin estimates.

As outlined in the IB, the non-clinical data for sex differences in PK measures are not clear and are contradictory. Allowing for a step wise dose escalation with adequate monitoring and PK based stopping limits is considered an appropriate means of conducting the study to allow for a comparison of PK across sexes and providing for the maximum chance of achieving full target engagement.

The C_{max} pharmacokinetic safety margin is based on the no-observed-adverse-effect-level (NOAEL) in the rat 3-month toxicity study. In this study GSK1144814A (vehicle, 5, 25 or 100 mg/kg/day) was given orally to rats for 13 weeks. There were no adverse, test-article related changes; therefore, the NOAEL was considered to be 100 mg/kg/day and corresponded to a geometric mean AUC of 95900 ng.h/mL and a geometric mean C_{max} of 6500 ng/mL. The use of rat data to determine C_{max} stopping criteria is felt to be acceptable as dose limiting toxicology in the most sensitive species (monkey) was related to total exposure (AUC) and not related to C_{max}, and there have been no adverse events (AEs) of concern related to C_{max} in the four Phase 1 clinical studies conducted thus far.

The study starting dose of 50 mg is anticipated to provide safety margins of approximately 12- and 14-fold respectively for AUC₀₋₂₄ and C_{max}. Subjects will be dosed and monitored in a controlled Phase 1 Unit clinic setting for the first 8 days of dosing and will only be escalated to the next cohort only when safety and PK data have been analyzed.

The target exposure of 14040 ng.h/mL (geometric mean AUC_{0-24} achieved with 200 mg daily dose in males for 28 days) gives a safety margin of approximately 3-fold against the 41900 ng.h/mL observed value while the predicted geometric mean C_{max} of 1836 ng/mL (at the 200 mg daily dose and after 14 days' administration) gives a safety margin of ~3.5 fold against the C_{max} .

No dose will be given that is expected to exceed a geometric mean AUC_{0-24} of 20950 ng.h/mL (2-fold safety margin).

As detailed in Section 10.7, the Safety Review Committee will evaluate safety and tolerability data from each cohort prior to escalating to the subsequent dose.

If study stopping criteria (see Section 9.9) have not been met and there are no concerning safety signals, the subsequent Cohort will proceed to the next dose.

If study stopping criteria are met, no further subjects will be dosed and the study will be terminated.

In the event that study stopping criteria have not been met, but the Safety Review Committee do not feel that it is appropriate to escalate to the next planned dose, the subsequent Cohort may be dosed at any of the previous dose levels, in order to confirm safety and PK data for this dose.

9.3 Allocation to treatment

The study will be conducted in a double-blind manner, with the subjects, Investigators and Sponsor all blinded to the treatment allocated. Both NT-814 and placebo will be presented as white capsules, identical in size and shape.

Following a 4-week screening period and confirmation of eligibility, subjects in each cohort will be randomized in a 3:1 ratio to receive either NT-814 or placebo. The IMP each subject will receive will be allocated by an Interactive Web Response Services (IWRS) tool provided by the Clinical Research Organization (CRO) on behalf of the Sponsor.

The dose will start at 50 mg for Cohort 1 and will increase in increments of 50 mg for the first 3 cohorts and for subsequent cohorts, the dose will be set based on tolerability and PK as deemed appropriate by the Safety Review Committee, up to a maximum of 400 mg.

9.4 Study treatment and administration

Subjects will be administered study medication in the morning, according to the randomization schedule, at the clinic on Day 1, through Day 8. On Day 8, subjects will be dispensed study medication for self-administration on Days 9 to 13 (1-2 days' overage should be included). On Day 14 subjects will be administered study medication on the morning of admission to the Phase 1 Unit. Subjects will be reminded to take the study medication at the same time each morning and to return

any unused medication when they return to clinic on Day 14. Subjects will be required to fast overnight prior to study drug administration on Day 1 through Day 14 (see Section 9.13.3).

9.5 Packaging and labelling

Investigational sites will be provided with bulk drug supplies (NT-814 50 mg capsules and matching placebo) in high-density polyethylene (HDPE) bottles packaged and labeled according to local regulatory requirements. Whilst in the clinic, doses will be prepared for the subjects each day. In-clinic doses can also be prepared in advance for convenience and stored in the secure area for dispensing each day. Upon discharge on Day 8 subjects will be provided sufficient capsules for dosing at home on Days 9 through 13, in HDPE bottles packages and labelled according to local regulatory requirements.

9.6 Handling and storage

Investigational product must be dispensed or administered according to procedures described in the Study Manual. Only subjects enrolled in the study may receive investigational product. Only authorized site staff may supply or administer investigational product. All investigational products must be stored in a secure area with access limited to the Investigator and authorized site staff. The investigational products must be kept in the original bottles and are to be stored at ambient room temperature up to maximum of 25°C. Maintenance of a temperature log (manual or automated) is required, whilst held at the study site.

9.7 Duration of subject participation

Subjects will be in the study for up to 7 weeks, from screening through to the final Follow-up phone-call assessment. During the study subjects will be required to attend the clinic on a total of 5 occasions, at Screening and for 8 continuous 24-hour assessment periods, then again on Day 14 for a 24-hour assessment, and as an outpatient for visits on the mornings of Days 16 and 17. A final Follow-up phone call will be conducted on Day 21. This will be replaced by a clinic visit if deemed more appropriate by the Investigator in order to follow up any ongoing AEs.

9.8 Discontinuation criteria

Subjects meeting any of the following criteria (regardless of treatment assignment) will be required to stop study medication and complete the early termination visit assessments:

- Intolerable complaints of undesirable sexual side effects from the study medication
- Oxygen saturation < 90% during a laboratory session that does not increase after administration of supplemental oxygen.
- If AST and ALT increase to ≥ 3 times the upper limit of normal
- Clinically relevant cardiovascular AE such as ventricular tachycardia or atrial fibrillation

- Signs of dehydration (e.g. orthostatic hypotension or decreasing urine outflow, impaired renal function or biochemistry profile change from the baseline, weight loss more than 10% from the baseline)

Subjects that discontinue early may be replaced.

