7.3 Exclusion criteria

The following exclusion criteria will apply to all subjects:

1. Any active comorbid disease deemed by the investigator to be clinically significant which could impact safety during study conduct including renal or hepatic impairment:
 - a) Serum creatinine laboratory value greater than 1.2 times upper limit of normal (ULN) reference range (after adjustment for age) at Screening or Day -1 or subjects with renal function glomerular filtration rate (GFR) $<60\text{mL}/\text{min}/1.73\text{m}^2$ based on the MDRD equation.
 - b) Total bilirubin greater than upper limit of normal reference range (with the exception of Gilbert's Syndrome) and/ or alanine transaminase (ALT) >2 times ULN reference ranges and/ or aspartate amino transferase (AST) >2 times ULN reference ranges, at Screening or Day -1.
2. Subjects with a prior medical history of or an increased risk of seizures, or who have a history of recent (within 6 months of Screening) head trauma that resulted in a loss of consciousness or concussion
3. Any prior or ongoing history of arrhythmias
4. Any ongoing cardiovascular disease including heart failure, coronary artery disease or uncontrolled hypertension or uncontrolled diabetes
5. Any clinically relevant ECG abnormalities at Screening
6. Unwillingness to refrain from eating grapefruit, grapefruit juice, Seville oranges, and pomelos from 7 days prior to admission on Day -1 until after their final follow-up visit
7. Use of any prohibited medications (see Section 9.13.2)
8. Any history of invasive malignancy in the past 2 years
9. Any active ongoing condition that could cause difficulty in interpreting vasomotor symptoms such as: infection that could cause pyrexia, pheochromocytoma, hyperthyroidism, carcinoid syndrome, alcohol abuse
10. Body mass index (BMI) $> 35\text{kg}/\text{m}^2$
11. Inability to complete questionnaires for any reason including psychiatric disorders and inability or unwillingness to use electronic devices
12. History of hypothalamic dysfunction.
13. Any clinically significant or unstable medical or psychiatric condition that would interfere with the subject's ability to participate in the study including anxiety syndromes
14. Any clinically significant abnormal laboratory test result(s) at Screening or on Day -1.

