9.9 Cohort and dose escalation stopping criteria

After each cohort a Safety Review Committee will review and assess all the available safety and PK study data from all of the cohorts to date in order to make a decision on the dose for the next cohort of subjects.

Data from a minimum of 14 subjects from the previous cohort must be reviewed before a decision to escalate can be taken.

The stopping criteria listed below apply to stopping during a cohort or at the end of a cohort during safety data review. Events that occur during the cohort will be passed onto the unblinded safety reviewers who will inform the study team of whether stopping criteria have been fulfilled and in such a case no other subjects will be enrolled. Subjects on treatment will be asked to stop dosing and if possible go through the early termination assessments.

1. One subject who has received NT-814 reports a serious adverse event which is considered at least possibly related to the NT-814
2. Two or more subjects, who have received NT-814, have QTc prolongation, defined as QTc > 500 ms for both Bazett and Fridericia corrections, or a prolongation from baseline of > 60 ms, confirmed (persistent for at least 5 min) during continuous ECG monitoring deemed to be at least possibly related to study drug (discovered at the end of the cohort during safety data review or on repeat ECGs taken during the study at the pre-determined time points or at the time of an AE)
3. Two or more subjects, who have received NT-814, have tachycardia, defined as resting supine heart rate > 125 beats per minute persisting for at least 10 minutes deemed to be unrelated to a hot flash episode and at least possibly related to study drug during continuous ECG monitoring (discovered at the end of the cohort during safety data review or on a repeat ECGs taken during the study at the pre-determined time points or at the time of an AE)
4. Two or more subjects, who have received NT-814, have symptomatic bradycardia, defined as resting supine heart rate < 45 beats per minute or asymptomatic bradycardia defined as resting supine heart rate < 30 beats per minute while awake persisting for at least 10 minutes during continuous ECG monitoring deemed to be at least possibly related to study drug (discovered at the end of the cohort during safety data review or on a repeat ECGs taken during the study at the pre-determined time points or at the time of an AE)

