5. Two or more subjects, who have received NT-814, develop hypotension, defined as an asymptomatic fall in Systolic blood pressure (SBP) > 20 mmHg to below 70 mmHg persisting for at least 10 minutes, or a symptomatic fall in resting supine SBP > 20 mmHg (excluding vasovagal reaction or associated with hot flashes) deemed to be at least possibly related to study drug
6. One or more subjects, who have received NT-814, fulfill Hy's law, defined as "an increase in AST or ALT ≥ 3 x upper limit of normal (ULN) and total bilirubin (TBL) ≥ 2 x ULN, where no other reason can be found to explain the combination of increases, e.g., elevated serum alkaline phosphatase (ALP) indicating cholestasis, viral hepatitis, another drug. The elevations do not have to be at the same time or within a specified time frame"
7. Two or more subjects, who have received NT-814, have > 3 x ULN of either ALT or AST, or > 2 x ULN for bilirubin or ALP deemed to be at least possibly related to study drug
8. Two or more subjects, who have received NT-814, have clinical and biochemical signs suggesting dehydration as assessed by the Investigator and Sponsor (weight loss $> 10\%$ from baseline, loss of skin turgor and biochemical signs such as increased serum urea and creatinine, high urinary osmolality and sediment) deemed to be at least possibly related to study drug
9. Two or more subjects, who have received NT-814, have sustained oxygen saturations below 90% that does not increase after administration of supplemental oxygen, deemed to be at least possibly related to study drug.
10. Two or more subjects, who have received NT-814, with clinically relevant cardiovascular AEs such as ventricular tachycardia or atrial fibrillation deemed to be at least possibly related to study drug
11. Dose escalation will not occur if the exposure of NT-814 is predicted to exceed a geometric mean AUC of 20950 ng.h/mL

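### The individual liver stop in Protocol 9.8 needs both AST and ALT at 3 x ULN, so a first subject with an isolated rise in one enzyme counts toward cohort criterion 7 but is not required to stop

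*Protocol*

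**What the plan says.** Protocol 9.8 lists individual discontinuation criteria. A subject who meets any one of them, on either treatment, "will be required to stop study medication and complete the early termination visit assessments". The liver criterion begins "If AST and ALT increase to" and sets the threshold at 3 times ULN or more.

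The other liver rules in the protocol act on one enzyme:

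- Exclusion 1b (section 7.3) joins ALT and AST, each above 2 x ULN, with "and/ or aspartate amino transferase (AST".
- Section 9.9, criterion 6 (Hy's law) needs one subject with "an increase in AST or ALT" to at least 3 x ULN, together with total bilirubin of at least 2 x ULN.
- Section 9.9, criterion 7 needs two or more NT-814 subjects with more than "3 x ULN of either ALT or AST", or with bilirubin or ALP above 2 x ULN, judged at least possibly related.

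When a 9.9 criterion is met, enrolment ends and subjects on treatment are asked to stop dosing. Section 7.4 points to 9.8 for required withdrawal and adds no liver threshold of its own. It lets the investigator withdraw a subject at any time and accepts laboratory results as grounds. Section 8.4 makes Day 8 discharge conditional on there being no safety concerns.

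**The concern.** Section 9.8 is there to fix a threshold at which a subject comes off drug without further debate. For transaminases that threshold is harder to reach than the one that counts her toward stopping the whole cohort, which is the wrong way round. Three other 9.8 criteria have a counterpart in 9.9: oxygen saturation (criterion 9), cardiovascular events (criterion 10) and dehydration (criterion 8). In each of those the individual rule is at least as broad as the cohort rule. Only the liver criterion is narrower on its main condition.

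The timing adds to this. Day 8 is both the day subjects go home with five days of capsules and the only scheduled on-treatment chemistry after which doses can still be withheld. A 9.8 stop would also bring the early termination assessments, which include chemistry. Without it, the next scheduled liver test is on the last dosing day. Protocol 5.4 reports no safety signals of note, but in 89 men and 1 woman, whereas this trial enrols only women.

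**Working it through.** The plan gives no figure to reproduce. The check is a comparison of the rules followed by simple dose arithmetic.

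**Test case.** The first NT-814 subject has ALT above 3 x ULN, AST below 3 x ULN and normal bilirubin and ALP. The rise is non-serious and judged possibly related.

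| Rule | Condition | Met? |
|---|---|---|
| 9.8 liver criterion | AST and ALT both ≥ 3 x ULN | No |
| 9.9 criterion 1 | one related SAE | No |
| 9.9 criterion 6 | AST or ALT ≥ 3 x ULN and bilirubin ≥ 2 x ULN | No |
| 9.9 criterion 7 | two or more subjects with ALT or AST > 3 x ULN | No: count is 1 of 2 |
| 7.4 withdrawal | investigator's judgement | Optional |
| 8.4 Day 8 discharge | no safety concerns | Judgement |

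No mandatory rule stops her. A single Hy's law case is covered by criterion 6. A related serious event is covered by criterion 1: "One subject who has received NT-814 reports a serious adverse event which is considered at least possibly related to the NT-814". A second subject like her would meet criterion 7.

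**How many subjects.** Section 9.9 has the committee review "all the available safety and PK study data from all of the cohorts to date", but does not say whether criterion 7 counts within a cohort or across the study. The gap therefore concerns one subject per cohort or one in the whole study.

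**Timing inputs.** Dosing runs from Day 1 to Day 14, with Days 9 to 13 at home (Protocol 9.1 and 9.4). Chemistry after the first dose is scheduled on Days 8 and 14, and at early termination (Protocol Table 2; SAP 4.10.2).

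**Doses left.** This assumes the Day 8 dose has been taken and the result is known before the Day 9 dose. The documents state no turnaround time.

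- Doses remaining: 14 − 8 = 6, five at home and one in clinic on Day 14.
- Share of the course: 6 / 14 = 42.9%.
- Each further day of delay removes one dose from this count.
- Days to the next scheduled chemistry: 14 − 8 = 6.

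**Further drug over six doses.**

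| Daily dose | Calculation | Total |
|---|---|---|
| 50 mg | 6 × 50 | 300 mg |
| 100 mg | 6 × 100 | 600 mg |
| 150 mg | 6 × 150 | 900 mg |
| 300 mg (Cohort 4, PK SAP section 3) | 6 × 300 | 1,800 mg |

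These totals measure exposure, not risk.

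**Room for extra discontinuations.** Section 9.9 states: "Data from a minimum of 14 subjects from the previous cohort must be reviewed before a decision to escalate can be taken". With 20 per cohort, 20 − 14 = 6 can be lost before the escalation review falls short, even with no replacements.

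**The case against.** The strongest reply is that this is a drafting looseness with several backstops. The 9.8 text does not contain the word *both*, and may simply name the two enzymes being monitored. Section 9.9 passes events during a cohort to unblinded safety reviewers. Sections 8.4, 9.12 and 10.7 allow individual unblinding for any safety concern. Most investigators would treat a possibly related enzyme above 3 x ULN as a reason not to discharge on Day 8. Nor does 9.8 mirror 9.9 in general: QTc prolongation, heart rate, and bilirubin or ALP have no dedicated individual criterion either. Fifteen subjects took 200 mg daily for up to 29 days, and this was considered safe and well tolerated. Finally, the proposed wording reaches further than the gap, because 9.8 has no relatedness condition.

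Much of this limits the point without removing it. The unblinded reviewers report whether a 9.9 criterion is met, and one case does not meet criterion 7. Unblinding, withdrawal and the discharge decision are all discretionary. If *and* was meant as *or*, the same correction is needed, and it keeps sites from applying the rule differently. The other mismatches between 9.8 and 9.9 are real and lie outside this point. The earlier 200 mg experience is reassuring, but it came from a database of 89 men and 1 woman, and the dose was below 300 mg. The remark on breadth stands: some unrelated rises would also lead to a stop. One example is an AST rise of muscle origin in a statin user, since statins are allowed under 9.13.2.

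**Conclusion.** The concern holds on the text as written. A first NT-814 subject with an isolated, non-serious, possibly related single-enzyme rise above 3 x ULN and bilirubin below 2 x ULN meets no mandatory stop, although she counts toward criterion 7. Found on Day 8, this leaves up to 6 of 14 doses and a 6-day interval without scheduled chemistry, unless someone chooses to intervene.

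The reach is small: one subject per cohort or one in the study, mainly at one blood draw. The documents give no rate for such rises, so no expected number of subjects can be stated. The dose count rests on the Day 8 result being available before the Day 9 dose. No endpoint or analysis changes. The correction is worth making because this is a mandatory safety threshold, it is out of line with its companion section, and putting it right is cheap.

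**What to change.** In Protocol 9.8, change the liver criterion to read: *If AST or ALT increases to ≥ 3 times the upper limit of normal*. Every subject counted under criterion 7 on a transaminase would then also meet the individual stop, because a value above 3 x ULN also satisfies the ≥ 3 x ULN threshold.

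If a two-enzyme rule is intended, give the reason in 9.8 and name who decides on a single-enzyme case before Day 8 discharge.

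The cost is one word, plus perhaps a few more individual discontinuations in either arm, some for unrelated rises. Section 9.8 allows these subjects to be replaced. The change does not deal with bilirubin or ALP under criterion 7, or with other 9.9 criteria that lack a dedicated individual rule, such as QTc prolongation.
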